1 ABBREVIATIONS USED IN THE PROTOCOL

Abbreviation	Term
AE	Adverse event
ASGE	American Society of Gastrointestinal Endoscopy
ALS	Aggregate specimen length
BMI	Body mass index
CA	California
CLD	Chronic liver disease
Cm	Centimeter
Co-I	Co-Investigator
CPT	Complete portal tracts
CRNA	Certified Registered Nurse Anesthetist
EUS	Endoscopic ultrasound
EUS-LB	Endoscopic ultrasound guided-liver biopsy
EGD	Esophagogastroduodenoscopy
FNA	Fine needle aspirate
FNB	Fine needle biopsy
g	Gauge
GIRB	Geisinger IRB
HRPO	Human Research Protection Office
In	Inches
Inc	Incorporated
IRB	Institutional Review Board
Lb	Pounds
LB	Liver biopsy
mm	Millimeters
PA	Pennsylvania
PI	Principle investigator
PLB	Percutaneous liver biopsy
PPT	Partial portal tracts
QASM	Quality and Safety Monitoring
SA	Specimen adequacy
SAE	Serious adverse event
SLB	Surgical liver biopsy
TLB	Transjugular liver biopsy
US	United States

Date Last Modified: 10/2/2017**IRB # 2017-0391****CONFIDENTIAL AND PROPRIETARY**

2 ABSTRACT

Chronic liver disorders (CLD) are a major cause of morbidity and mortality for individuals in the US. Though serologic analysis will often lead to a conclusive diagnosis, liver biopsy remains an important method for helping to determine the etiology and stage of LD. Percutaneous liver biopsy (PLB), transjugular liver biopsy (TLB) and surgical liver biopsy (SLB) are alternative methods for obtaining hepatic tissue. In recent years endoscopic ultrasound guided-liver biopsy (EUS-LB) has come to the forefront as a safe and effective method for obtaining tissue in CLD. There are several studies of the safety of EUS-LB as well as the adequacy of specimens obtained in this fashion. Most studies involve a 19-g needle, therefore in this study we hope to compare the tissue yields of a 19-g FNB needle, in comparison to conventional 19-g FNA needle. We predict that 19-g FNA and 19-g FNB needle will demonstrate similar diagnostic accuracy, with less visible blood artifact. Similarly, we predict the safety to be equal.

3 BACKGROUND AND SIGNIFICANCE

Chronic liver disease has a number of causes, and leads to significant mortality and morbidity in the United States. It has been estimated that roughly 36,000 individuals die annually from the burden of chronic liver disease, thus early diagnosis and intervention are paramount to preventing such complications [1]. Though serologic markers and non-invasive diagnostic imaging modalities are used as a method for determining the underlying disease process, these methods lack the specificity of determining etiology of a patient's chronic liver disease [2-5]. Therefore, liver biopsy remains the "gold standard" for obtaining valuable diagnostic and prognostic information.

At present there exist several methods for liver tissue acquisition. The most widely accepted method remains percutaneous route (PLB), which utilizes percussion or imaging to localization the biopsy site [6-8]. The issue with this approach is its potential complication of post-procedural pain in up to 84%, bleeding in 1/2500-10,000 procedures, with under 1/10,000 of these cases being fatal [7-17]. Another means for obtaining tissue samples is the transjugular route (TLB), which also allows for portal pressure measurement, and is usually reserved for patients with coagulopathy[18,19].

More recently, endoscopic ultrasound guided liver biopsy (EUS-LB) has been developed as a newer LB technique [23, 24]. The feasibility of EUS-LB for liver lesions has been validated yielding excellent diagnostic results in several studies [25-27]. This technique has also been evaluated for hepatic parenchymal disease with up to 90% diagnostic yield. Subsequently, EUS-LB using a 19-g needle was compared to percutaneous/transjugular routes showing at least comparative, and in some instances improved sample acquisition, versus other methods [28]. Different 19-g needles have been utilized in this setting yielding variable diagnostic specimens [29-33]. However, there has yet to be comparison of 19-g FNA versus a 19-g core biopsy needle for EUS-LB.

Primary End Points

1. Proportion of cases for which a histologic diagnosis could be made based upon the amount of tissue obtained with the needle.
2. Number of portal tracts (PT) in the specimen. [34-36]
3. Aggregate specimen length (ASL), length of the longest piece (LLP), and degree of fragmentation.

Secondary End Points

1. Presence of a visible core specimen.
2. Presence of visible clots in specimen.
3. Adverse events (AE) and serious adverse events (SAE).

Date Last Modified: 10/2/2017

IRB # 2017-0391

CONFIDENTIAL AND PROPRIETARY

4 HYPOTHESIS AND SPECIFIC AIMS

4.1 Hypothesis

We predict that the 19-g FNA needle and 19-g FNB needle will have similar ability to obtain adequate EUS-LB specimens

4.2 Specific Aim 1

To determine the adequacy of EUS-LB using a 19-g FNB needle as compared with 19-g FNA needle.

4.3 Specific Aim 2

To determine if the 19-g FNB needle will demonstrate less blood artifact during the time of EUS-LB as compared with 19-g FNA needle.

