6.8.1 Statistical Analysis Plan

Assuming the 19-g FNB needle has a success percentage of 98% (ie, ≥ 5 portal triads), and margin over FNA needle of 5% (98% vs. 93%), the study needs to evaluate 32 patients to achieve 80% power for a 1-sided non-inferiority test. This also assumes each patient provides 2 specimens. If the margin is increased to 10% (98% vs. 88%), then the study needs to evaluate 18 patients to achieve 80% power.

Descriptive statistics will be utilized to represent continuous and categorical variables, with results expressed as medians with ranges. Multiple comparisons between the aggregate tissue length and CPT yield from bilobar, left lobe only, and right lobe only biopsies will be carried out using the Mann-Whitney-Wilcoxon test. A P-value of <0.05 will be considered statistically significant.

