6.8.2 Statistical Power and Sample Size Considerations

The purpose of this study to determine if the 19-g FNB EUS needle provides liver cores equal or superior to 19-g FNA needle for histologic interpretation. A few preliminary cases utilizing the 19g core needle have been found to provide adequate cores. It is felt that 32 cases collected prospectively should be adequate to learn how the 19g FNB needle compares to the 19g FNA needle in different patients with different liver conditions.

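### The adequacy hypothesis is 'similar', but the only sized test is one-sided non-inferiority, which cannot show similarity; no superiority step is given either

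*Combined protocol and SAP*

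**What the plan says.** Section 4.1 states the hypothesis as "We predict that the 19-g FNA needle and 19-g FNB needle will have similar ability to obtain adequate EUS-LB specimens". Section 2 (abstract) predicts that the needles "will demonstrate similar diagnostic accuracy". Neither gives a margin, a direction or a test.

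Section 6.8.2 gives the purpose as finding out whether the FNB needle "provides liver cores equal or superior to 19-g FNA needle for histologic interpretation".

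Section 6.8.1 sizes the trial at 32 patients "to achieve 80% power for a 1-sided non-inferiority test". Success there means at least 5 portal triads. FNB is taken as 98%, the margin is 5 points (98% v 93%), and each patient gives 2 specimens. A 10-point margin (98% v 88%) is said to need 18 patients.

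The analysis paragraph of the same section names only descriptive statistics, Mann-Whitney-Wilcoxon comparisons of tissue length and portal tract yield by lobe, and a general 0.05 threshold. It contains no non-inferiority analysis, no one-sided alpha, no superiority test, and no rule linking a result to a conclusion.

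**The concern.** Taken as a claim that data could confirm or refute, 'similar' requires the difference between needles to be bounded on both sides. A one-sided non-inferiority test bounds one side only. With FNB as the new needle, it becomes easier to pass the further FNB pulls ahead, which is exactly when 'similar' is untrue. A pass is therefore not evidence for the hypothesis in section 4.1.

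The purpose in section 6.8.2 also leaves room for a finding that FNB is better, yet no test is planned to support one. As written, the plan does not fix in advance which conclusion a given result allows: not inferior, similar or superior.

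**Working it through.** **Inputs from the plan.** 32 patients (6.2.1, 6.8.1); 2 specimens per patient, FNB 98%, comparison rates 93% and 88%, margins 5 and 10 points, one-sided test, 80% power (all 6.8.1).

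**Assumptions.** 1:1 allocation (ratio not stated), so 16 patients and 32 specimens per needle; specimens independent; difference taken as FNB minus FNA with FNA as reference; one-sided alpha 0.05 (not stated for this test), with 0.025 as a check.

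**The plan's own figure.** Specimens per needle n = [p_B(1−p_B) + p_A(1−p_A)] × (z_0.95 + z_0.80)² / (p_B − p_A + margin)², where B is FNB, A is FNA, and (1.645 + 0.842)² ≈ 6.183. With 2 specimens per patient and 1:1 allocation, total patients equal specimens per needle.

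- Both needles 98%, 5 points: 0.0392 × 6.183 / 0.05² = 96.9, so 97.
- 98% v 93% as true rates, 5 points: (0.0196 + 0.0651) × 6.183 / 0.10² = 52.4, so 53.

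Neither gives 32, and no single variant tried gave both 32 and 18. That is a separate matter; the calculations below take 32 specimens per needle as given.

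**Operating characteristics.** All 33 × 33 outcome tables were enumerated and weighted by their binomial probabilities. Each bound was tested with a score statistic using restricted maximum-likelihood estimates, at one-sided 0.05.

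| True rates, FNB v FNA | Non-inferiority passes, 5 points | Similarity within ±5 passes |
|---|---|---|
| 98% v 98% | 25.8% | 0.0% |
| 98% v 93% | 61.4% | 0.0% |
| 98% v 88% | 81.2% | 0.0% |
| 98% v 80% | 95.2% | 0.0% |

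At one-sided 0.025 the non-inferiority column becomes 7.1%, 41.4%, 68.4% and 90.7%, and similarity stays at 0.0%.

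**Why similarity within ±5 cannot pass.** The most favourable table is no failures with either needle. The restricted estimates are then 0.95 and 1, so z = 0.05 / √(0.95 × 0.05 / 32) = 0.05 / 0.0385 = 1.30, and p = 0.097 on each side.

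At ±10 points, similarity passes 27.4% of the time at 98% v 98%, 5.1% at 98% v 93% and 0.9% at 98% v 88%. By the normal formula, equivalence at ±5 points with both needles at 98% and 80% power needs 0.0392 × (1.645 + 1.282)² / 0.05² ≈ 134.3, so 135 specimens per needle.

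**A superiority step after non-inferiority.** At 98% v 88% it succeeds in about 52% of trials with an uncorrected pooled z test and 21% with Fisher's exact test. At 98% v 93% the figures are 23% and 4%.

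**One result under each reading.** FNB 32/32, FNA 28/32, 5-point margin: non-inferiority p = 0.006; upper bound for similarity p = 0.94; superiority one-sided p = 0.019 with the pooled z test and 0.057 with Fisher's exact test.

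**The case against.** The strongest reply is that 'similar' is plain language in a prediction and may mean only 'not inferior'. That may be so: section 4.1 never says two-sided. If so, the remedy is to write what is meant, because the word as it stands claims more than the sized test can deliver.

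A reader might go further and infer that three sections give three conflicting sidednesses. The documents do not support this. Only section 6.8.1 states a sidedness, and the purpose in section 6.8.2 is ordinary wording for a non-inferiority aim. The mismatch is with 'similar'; the gap at 6.8.2 is the missing superiority step.

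A reader might also infer that one data set could be reported as either 'similar' or 'superior' under this plan. The plan names no superiority test, a non-inferiority pass does not permit that claim, and the 32/32 v 28/32 example reaches superiority with the z test but not with Fisher's exact test. Nor do the documents say how a pass would be reported.

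Two further objections stand in part. The near-zero chance of showing similarity within ±5 points largely reflects the trial's size; still, the sidedness problem would remain in a larger trial. And a superiority step added to a test that the analysis paragraph never specifies would leave the larger gap open, so the fix has to cover both.

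**Conclusion.** The concern holds in this limited form. The sized test cannot support the 'similar' of sections 2 and 4.1. Its chance of passing rises from 26% when the needles are equal at 98% to 81% at 98% v 88%, while similarity at the plan's 5-point margin is out of reach with 32 specimens per needle. The purpose in 6.8.2 agrees with non-inferiority but lacks a test for its superiority half, and the sized test is missing from the analysis paragraph.

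The percentages rest on 1:1 allocation, the score test, one-sided 0.05 and independent specimens. Section 6.5 takes both specimens from one patient, one per lobe; positive correlation between them would leave less information than 32 independent specimens per needle. The pattern is the same at one-sided 0.025. The trial can still run, but what it may conclude should be settled before analysis.

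**What to change.** 1. **Sections 4.1 and 2.** Restate the adequacy hypothesis as: the success rate (at least 5 portal triads) with FNB is not lower than with FNA by more than the stated margin. Say how this endpoint relates to the primary endpoints in 6.6, none of which is defined by that threshold. In the abstract, do not present similar diagnostic accuracy as something this test shows.
2. **Section 6.8.1, analysis paragraph.** Specify the non-inferiority test, its one-sided alpha, and a method suited to few failures and two specimens per patient. Then add, in fixed sequence, a superiority test on the same endpoint at the same one-sided alpha, with its method named. If prespecified, this needs no alpha adjustment within that endpoint. State that its power is low and depends on the test chosen.
3. **Reporting rule.** Report a pass as 'FNB not inferior'. Use 'similar' only if the two-sided interval matching the alpha (90% for one-sided 0.05) lies wholly within ± the margin.

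The cost is a few sentences and one extra test, with no added patients, procedures or data. The trial gives up the word 'similar' unless the interval earns it.

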5 PRELIMINARY DATA

Our EUS group has used the 19-g EUS FNB needle in several patients undergoing EUS-guided liver biopsy, and cores of liver tissue can be obtained. We have found that special tissue handling after biopsy is required to prevent fragmenting the tissue. We have improved the technique of tissue handling, and can minimize post-biopsy fragmentation. This can allow a better comparison of different needle gauges.

6 STUDY DESIGN

6.1 Description

This is a prospective randomized trial comparing the biopsy specimen adequacy (SA) of 19-g FNA versus 19-g FNB needle for EUS-LB.

6.2 Study Population

6.2.1 Approximate Number of Subjects

Approximately 32 subjects will participate in this study.

6.2.2 Inclusion Criteria

1. Patients undergoing EUS-LB
2. Platelet count \geq 50,000
3. International normalized ratio (INR) $<$ 1.5
4. Age $>$ 18 years

Date Last Modified: 10/2/2017

IRB # 2017-0391

CONFIDENTIAL AND PROPRIETARY

5. Non-pregnant patients

6.2.3 Exclusion Criteria

1. Age < 18 years
2. Pregnant patients
3. Inability to obtain consent
4. Anticoagulants or anti-platelet agents use (excluding aspirin) within the last 7-10 days
5. Platelet count < 50,000
6. INR \geq 1.5
7. Presence of ascites
8. Known liver cirrhosis
9. Hemophilia

6.3 Recruitment

Patients shall be recruited in the pre-procedural endoscopy area. After identifying subjects, a study investigator shall discuss the study in detail in person. The patient will be given time to read the consent form and ask questions.

6.4 Study Duration

6.4.1 Approximate Duration of Subject Participation

Participation is just for the duration of the EUS-LB.

6.4.2 Approximate Duration of Study

The duration of the study shall last until 6 months from enrollment of the last study participant. This shall allow for analysis of final data points and construction of a manuscript.

6.5 Procedures

EPIC electronic health records database will allow for availability of demographic data and office-based follow-up records. ProVation MD software information will provide details regarding endoscopic parameters and intervention performed.

Electronic records gathered for study purposes will only be available to study investigators and will be stored on an encrypted hard drive on a computer. Data will initially be entered with PHI attached so that all information can be obtained. Once all data collection is complete identifiers will be removed and random number assigned to the patients.

Upon initial encounter, the study shall be described to the patient in detail by one of the study investigators and informed consent obtained.

Date Last Modified: 10/2/2017

IRB # 2017-0391

CONFIDENTIAL AND PROPRIETARY

Once the patient has agreed to participate, demographic data will be obtained from the medical record including; age, gender, height [inches (in)], weight [pounds (lb)], body mass index (BMI) (lb/in²), past medical history [in particular diagnosis of liver disease, biliary or pancreatic disease, ascites, encephalopathy, portal hypertension, portal hypertension-related bleeding (i.e. varices), liver cancer or masses]. Past surgical history shall be obtained regarding prior cholecystectomy, hepatobiliary or pancreatic surgery (i.e. pancreatojejunostomy) or bariatric surgery (i.e. Roux-en-Y gastric bypass). Medication and social history shall be performed regarding alcohol intake per week and hepatotoxic medications (i.e. acetaminophen). A baseline INR and platelet count shall be performed on all individuals prior to EUS-LB, as is the standard of care.

EUS-LB Protocol

Patients undergoing EUS-LB receive anesthesia during the procedure, as per normal practice. This is provided by a certified registered nurse anesthetist (CRNA). The endosonographic study will be conducted with a linear array echoendoscope (GF-UC140-AL5; Olympus America, Center Valley, PA). Before needle puncture of the desired lobe, color Doppler imaging will be used to ensure the lack of vascular structures in the trajectory of the needle. The EUS-LB will be performed in widely separated regions of the liver using a 19-g EUS-FNA needle (Expect Flexible 19g, Boston Scientific, Marlborough, MA) or a 19-g FNB needle (Acquire 19g, Boston Scientific, Marlborough, MA). A computer-generated randomized schema shall determine needle type selection.

The left lobe is described as liver parenchyma identified a few centimeters below the gastroesophageal junction with the echoendoscope torqued clockwise. The right lobe is considered the large area of liver tissue can be seen through the duodenal bulb, near the gallbladder [37]. The stylet is removed, heparin flushed through the needle lumen, and the suction device set and attached to the needle hub. The prepared needle is then inserted into the echoendoscope. A transgastric approach will be used to obtain samples from the left lobe of the liver; a transduodenal approach, with the linear echoendoscope positioned in the duodenal bulb, will be used to obtain samples from the large amount of liver parenchyma seen in that location. Once adequate liver parenchymal penetration will be achieved with the needle (~2-6 cm), full suction will be applied with a 20-mL vacuum syringe. One pass consists of a total of 7 to 10 to-and-fro needle motions with the fanning technique applied under direct and continuous endosonographic visualization of the tip of the needle.

The needle will then be removed from the echoendoscope. The specimen will be pushed from the needle with the stylet directly into a microseive, and blood washed from the specimen with a gentle saline rinse. The endosonographer looks for multiple pieces of light brown tissue approximately 5 to 15 mm in length. The tissue cores are then “floated” off the microseive into formalin solution. Heparin is flushed through the needle lumen prior to the next pass. The biopsy process is then repeated on the opposite liver lobe. A pass per liver lobe will be performed in each patient; using the standard 19-g EUS-FNA needle or the 19-g EUS FNB

Date Last Modified: 10/2/2017

IRB # 2017-0391

CONFIDENTIAL AND PROPRIETARY

needle. All patients are closely observed in the recovery area for 1 hour after the procedure, as per our standard policy. Patients will be followed-up with by a phone call the next day and at 1 week after the procedure, as per standard of care.

Sample Processing

The surgical pathology department, per a specific protocol for clinical practice, will process the EUS-LB samples. Tissue samples are left in formalin for at least 1 hour before processing. The contents of the formalin jar will be poured into a petri dish, and visible cores of liver tissue picked out with small forceps by the surgical pathology technician. These pieces are arranged in a linear fashion on lens paper, then the specimen photographed alongside a ruler to estimate pre-processing tissue lengths. Samples from both lobes and the different needles will be submitted for evaluation separately. The tissue will be processed in standard fashion, and slide blanks made (5- μ m tissue thickness). These blanks are stained with hematoxylin and eosin, trichrome, and reticulin, with other special stains done as needed. The slides are digitized using a whole slide scanner (ScanScope CS; Aperio Technologies, Inc, Vista, CA), and the digitized images used for quantitative analysis (eSlide Manager; Aperio Technologies, Inc). Quantification of sample length (mm) and portal triads is performed by 2 of the investigators, annotating the digital images with the software. Fellowship-trained GI pathologists then perform histologic interpretation for clinical use.

Post-Procedural Follow-up

After undergoing the procedure, patients will receive a 1 week follow-up phone call to monitor for adverse events (i.e. bleeding), as per standard of care.

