6.6 Primary Endpoints

1. Proportion of cases for which a histologic diagnosis could be made based upon the amount of tissue obtained with the needle.
2. Number of portal tracts (PT) in the specimen [34-36]

Date Last Modified: 10/2/2017

IRB # 2017-0391

CONFIDENTIAL AND PROPRIETARY

3. Aggregate specimen length (ASL), length of the longest piece (LLP), and degree of fragmentation

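### No masking to needle is specified for the two investigators who count portal triads and measure length on the digitised slides; reading coded copies is a cheap improvement

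*Combined protocol and SAP*

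**What the plan says.** Under Sample Processing, Section 6.5 assigns the research measurements: "Quantification of sample length (mm) and portal triads is performed by 2 of the investigators, annotating the digital images with the software". The slides have by then been digitised. The clinical reading is a separate step: "Fellowship-trained GI pathologists then perform histologic interpretation for clinical use".

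The measurements bear on three places. Section 6.6 lists the number of portal tracts as primary endpoint 2 and, as primary endpoint 3, "Aggregate specimen length (ASL), length of the longest piece (LLP), and degree of fragmentation". Section 6.8.1 bases the sample size on a success criterion of at least 5 portal triads, with 98% against 93% and a 5-point margin.

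Length has a second possible source. Before processing, the cores are laid out, "then the specimen photographed alongside a ruler to estimate pre-processing tissue lengths". The document does not say whether the length endpoints come from the photographs or from the slides.

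On handling, Section 6.5 says: "Samples from both lobes and the different needles will be submitted for evaluation separately". It does not say how slides or images are labelled. On coding, Sections 6.5 and 6.9.1 both say: "Once all data collection is complete identifiers will be removed and random number assigned to the patients". Sections 8.2 and 8.3 also give subjects a random number, as a privacy measure and without timing, and restrict access to study data to the project investigators.

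**The concern.** The endosonographer must know which needle is in use, so the biopsy itself cannot be masked. The slide reading can be, and the plan does not say that it will be.

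Counting portal triads takes judgement. The abbreviation list has both complete and partial portal tracts; Section 6.5 counts triads, Section 6.6 tracts, and Section 6.8.1 complete portal tracts. No rule settles borderline structures. Marking tissue ends for length also takes some judgement, though less, and it can be re-measured on the stored image. The readers belong to a team with stated expectations: similar adequacy (Section 4.1) and less blood artifact (Section 2, with Section 4.3 as the aim). A reader who knew the needle could settle doubtful cases differently in the two arms. At stake is the credibility of one primary endpoint, part of another, and the outcome used for planning.

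**Working it through.** **1. Is masking stated anywhere?** The document does not mention blinding or masking of anyone, needle-neutral labels, or reading without access to allocation. The provisions that come closest are these:

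| Provision | Section | What it does | Does it conceal the needle from the readers? |
|---|---|---|---|
| Random number after data collection | 6.5, 6.9.1 | Replaces patient identifiers | Not stated; the readings are themselves data, so the number follows them |
| Random number, no timing given | 8.2, 8.3 | Protects confidentiality | Not stated |
| Data access for project investigators only | 8.2, 8.3 | Keeps outsiders out | Silent on what each investigator may see |
| Separate submission by lobe and needle | 6.5 | Keeps specimens apart | Labelling not described |

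None of these is a masking measure. Equally, none shows that the readers will see the allocation.

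**2. Which endpoints depend on the readers?**

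- Primary endpoint 2 and the success criterion of at least 5 triads depend on them directly.
- The length parts of primary endpoint 3 depend on them so far as slide lengths rather than photographs are used.
- No assessor is named for degree of fragmentation.
- Primary endpoint 1 rests on a histologic diagnosis, and histologic interpretation is assigned to the GI pathologists. It lies outside this point, although no masking is stated there either.

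**3. Scale of one reading.** This shows how sensitive the result is. It does not estimate bias.

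- Patients: about 32 (Sections 6.2.1 and 6.8.1).
- Specimens per patient: 2 (one pass per lobe in Section 6.5; also assumed in Section 6.8.1).
- Specimens: 32 × 2 = 64.
- Allocation ratio: not stated; 1:1 assumed, so 64 / 2 = 32 specimens per arm.
- One specimen whose recorded result crosses the threshold: 1/32 = 3.1 points.
- Two such specimens: 2/32 = 6.25 points.
- Stated margin: 5 points.

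The plan does not say whether both readers read every specimen or how two readings are combined. The shift therefore refers to the result finally recorded.

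**4. Workload of coding.** Section 6.5 names three routine stains: "These blanks are stained with hematoxylin and eosin, trichrome, and reticulin".

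- One stain read per specimen: 64 × 1 = 64 images.
- All three scanned, one slide each (assumption): 64 × 3 = 192 images, and more with special stains.
- Ruler photographs, if used for length, one per specimen (assumption): 64.
- Total with three stains and photographs, before special stains: 192 + 64 = 256.

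Coding the images does not change the sample size.

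**The case against.** The strongest objection is that the point rests on silence. The pathology department processes the samples under its own protocol, which is not supplied and may settle slide labelling. The readers may be masked in practice. If the privacy numbering in Sections 8.2 and 8.3 were applied before reading, a reader could not readily look up the needle. Tissue appearance may reveal the needle in any case, and the technician's selection of visible cores comes before any image that could be coded.

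Much of this stands, and it rules out several stronger readings that a reader might infer:

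- **That the readers know the needle.** The document does not say so. The access rule restricts outsiders and does not say that each investigator sees the allocation.
- **That separate submission puts the needle on the label.** The sentence does not say that. Section 6.5 reads most naturally as one needle type per patient, so samples from different needles would be apart anyway.
- **That concealment is excluded.** The sections differ on when numbers are assigned, so the matter is unresolved.
- **That a planned needle test is shown to be distorted.** Section 6.8.1 applies the Mann-Whitney-Wilcoxon test to bilobar, left-lobe and right-lobe comparisons. It names no needle comparison for that test, and nothing here relies on it.

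The objection does not remove the gap. The pathology protocol is described as one for clinical practice and is cited for processing, whereas investigators do the research quantification. If masking is already the practice, one added statement records it. Imperfect masking is still better than none specified.

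**Conclusion.** The point holds as a design improvement. The plan contains no contradiction here, and no biased result has been shown. Two study investigators read a judgement-based primary endpoint in a needle comparison, and the document does not mask them to needle. The random numbers are confidentiality measures and do not fill that gap.

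The direction and size of any bias cannot be derived: the document gives no reader variability, no distribution of counts and no labelling details. The figure of 3.1 points per specimen against a 5-point margin shows only that few readings need to change to matter. It rests on 64 specimens and assumed 1:1 allocation. The case is strongest for triad counts and weaker for length.

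**What to change.** In Section 6.5, Sample Processing, directly after the sentence that assigns quantification to the two investigators, add:

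> For the research quantification, copies of the digital images are labelled with a random code that conceals needle and patient. The code is assigned and held by a member of the study team with authorised data access who is not one of the two readers. The readers have no access to allocation, and readings are locked before the code is linked to patient, lobe and needle. Clinical slides and the pathologists' clinical interpretation are unaffected and need not wait for the research reading. If the ruler photographs supply any length endpoint, they are coded and measured in the same way.

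Using copies keeps the clinical reading free of delay. Naming an authorised code-holder keeps the step consistent with the access rule in Sections 8.2 and 8.3.

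**Cost.** The cost is a small relabelling task, at the volumes worked out above, with no extra reader, procedure or patient.

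**Limits.** Masking may be incomplete if tissue appearance suggests the needle; Aim 2 itself asks whether blood artifact differs. The technician's earlier selection of cores and primary endpoint 1 are not covered by this change.
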